8.2 Clinic visits

Table 8.2 Overview of the procedures during each visit

Procedure	Preoperative	Baseline and Intervention	6 month Follow-up	12 month Follow-up	24 month Follow-up	36 month Follow-up
Time	D-1	D-0	M 6	M 12	M 24	M 36
Patient information		X				
Oral examination	X	X	X	X	X	X
Informed consent	X					
Medical history	X					
Inclusion and exclusion criteria	X					
Selection of eligible lesions		X				
Caries risk assessment	X					
Hot-cold sensitivity assessment	X	X	X	X	X	X
Dental examination	X	X	X	X	X	X
Radiographic examination		X		X	X	X
Assessment of lesion activity						
Randomization		X				
Intervention (Infiltration)		X				
Photographic documentation of lesions	X	X	X	X	X	X
Record of adverse effects			X	X	X	X
Instruction for oral health care		X	X	X	X	X
Color match		X	X	X	X	X
Discoloration		X	X	X	X	X
Surface Integrity		X	X	X	X	X
Secondary Caries		X	X	X	X	X

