11.4 Statistical Analysis

11.4.1 Descriptive Statistics

For the digital subtraction procedure, the ANOVA for Repeated Measures, will be used to determine significance between the two groups ($p=.05$). The remaining endpoints will be listed as percentages rather than subjected to statistical analyses.

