A previous infiltration study by Martignon et al. [5] reported a 3-year difference of proportions of 37.8% (95%CI: 20.5-55.2%) with (resin infiltration (68%) vs. control (30%)). Based on this and with alfa = 0.05 and a power of 80% the calculated sample size (t-test; matched pairs) would be 23 lesion pairs (thus 23 participants) to find significant differences. However, this study aimed to enroll 150 participants to not only allow for a potentially high attrition rate (20%) over a period of 3 years, but also aiming to better quantify the efficiency of the treatment effect.

Statistical Analysis

All evaluations are performed by two trained and calibrated examiners. The primary outcome is proportion of lesions that required restorative treatment (filling) after 3 years as measured via dental examination. Differences between groups will be tested using Fisher's exact test and ANOVA for Repeated Measures for subgroup analysis based on caries risk. Secondary outcomes are change in categorical lesion depth (progression to next depth category lesion; E1->E2->D1->D2->filling) after 6 months and 1, 2 and 3 years as measured by pairwise comparison of radiographs as well as the influence of Icon treatment on clinical parameters. Differences will be analyzed with McNemar's test with 95% confidence interval (95% CI) and P = .05.

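### The SAP's repeated-measures ANOVA for the caries-risk subgroup of a yes/no outcome can misstate its error rate, in either direction, if filling rates and subgroup sizes both differ by risk

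*Combined protocol and SAP*

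**What the plan says.** The SAP, under Statistical Analysis, states: "The primary outcome is proportion of lesions that required restorative treatment (filling) after 3 years as measured via dental examination". It continues: "Differences between groups will be tested using Fisher's exact test", and the same sentence adds "ANOVA for Repeated Measures for subgroup analysis based on caries risk". It does not name the model term, the repeated factor, the risk categories or the expected subgroup sizes.

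Protocol 11.4.1 uses the same method for something else: "For the digital subtraction procedure, the ANOVA for Repeated Measures, will be used to determine significance between the two groups". It then says: "The remaining endpoints will be listed as percentages rather than subjected to statistical analyses". The protocol therefore gives no model for applying this ANOVA to fillings.

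Table 8.2 of the protocol lists "Caries risk assessment" at the preoperative visit only, while sections 1.4 and 6.4 say caries risk is followed every six months. Section 8.3 lists the information that feeds into risk status but gives no rule or cut-off for combining it. Section 4.2 frames both hypotheses in a high-caries-risk population.

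**The concern.** Filling status at 3 years is one binary value per lesion. In a split-mouth design the only repeated factor for that outcome is tooth within patient. A treatment-by-risk test in this ANOVA assumes that the within-patient treatment difference has the same variance in both risk groups. For a binary outcome that variance follows from the filling rates, and a caries-risk classification is meant to separate patients with different rates. If it succeeds and the groups differ in size, the test uses the wrong standard error.

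At stake is whether a statement that infiltration works better, or no better, in higher-risk patients can be trusted. The main comparison of infiltrated with control lesions is not affected.

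**Working it through.** **Inputs from the documents.** Protocol 11.2 enrols 150 patients and expects 20% loss: 150 × 0.80 = 120 at 3 years, which matches its own figure. Each patient contributes one infiltrated and one control lesion. The SAP's significance level is 0.05; sidedness is not stated, and two-sided is assumed. The SAP gives no error rate or power for the subgroup test. Its 23-pair calculation concerns the overall comparison and has no bearing here.

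**Assumed inputs.** Filling rates by risk group, subgroup sizes, independence of the two lesions within a patient, and treatment-by-risk as the tested term.

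**Step 1: what the test is.** Let D = control minus infiltrated filling status, so D is -1, 0 or +1. With two lesions per patient, the ANOVA treatment-by-risk F equals the square of the pooled-variance two-sample t on D. A numerical check on one simulated dataset gave 0.3297 for both.

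**Step 2: variance of D.** Var(D) = pc(1 − pc) + pt(1 − pt), where pc and pt are the control and infiltrated filling risks. With no treatment effect:
- high risk, 25% in both arms: 2 × 0.25 × 0.75 = 0.375
- low risk, 5% in both arms: 2 × 0.05 × 0.95 = 0.095

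**Step 3: true against assumed variance of the contrast.** True: 0.375/nH + 0.095/nL. Assumed by the ANOVA: pooled variance × (1/nH + 1/nL). The critical value on 118 df is 1.98.
- 30 high/90 low: true 0.01356. Pooled (29 × 0.375 + 89 × 0.095)/118 = 0.1638, times 0.04444 = 0.00728. The true SE is √(0.01356/0.00728) = 1.36 times the assumed one, so the effective cut-off is 1.98/1.364 = 1.45 and the rejection rate about 15%.
- 60/60: true and assumed are both 0.00783; about 5%.
- 90 high/30 low: true 0.00733, assumed 0.3062 × 0.04444 = 0.01361. The ratio of SEs is 0.734, the effective cut-off 2.70 and the rejection rate about 0.7%.

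Simulation agrees:

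| High/low | 24/96 | 30/90 | 40/80 | 60/60 | 80/40 | 90/30 |
|---|---|---|---|---|---|---|
| Null rejection, 25% vs 5% | 18% | 16% | 11% | 5% | 1.6% | 0.8% |

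An unequal-variance test on the same differences holds 4.7% to 5.2% at all splits tested.

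**Step 4: dependence on the filling rates.** With 20% and 10%, the figure at 30/90 is 9.3%. With 15% in all cells it is 4.8% to 5.3% from 24/96 to 96/24. Using the 3-year progression rates quoted in protocol 4.3.4 as stand-ins (42%/4% for low risk, 70%/32% for high risk), the variances are 0.282 and 0.428, a ratio of 1.52. The error rate then runs from 3.0% at 90 high/30 low to 7.7% at 30 high/90 low. Those are progression rates, not filling rates.

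**Step 5: power when most patients are high risk.** Assume filling of 40% control and 15% infiltrated in high-risk patients, and 5% in both arms in low-risk patients, with 90 high/30 low. The difference in effects is 0.25. True SE = √(0.3675/90 + 0.095/30) = 0.0851. The ANOVA's SE is √(0.3005 × 0.04444) = 0.1156, so it needs a difference of 1.98 × 0.1156 = 0.229. Power is Φ((0.25 − 0.229)/0.0851), about 60%. An unequal-variance test has about 82% in simulation.

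**The case against.** The strongest reply is that the documents fix none of the quantities that produce a bad error rate. That stands. A reader might infer that the false-positive rate runs from under 1% to 18% as a property of this plan, driven by subgroup sizes alone. The documents do not support that: both filling rates and sizes must differ, and Step 4 shows rates near 5% or between 3% and 8% under other inputs.

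A reader might also infer that the subgroup result would give false support to the high-risk claim. Every inflated figure needs high-risk patients to be the minority. Section 4.2 describes the trial population as high risk, which points the other way, to a conservative test. The hypotheses are tested by the main comparison, not by this subgroup. The inclusion criteria in 7.2.1, however, set no caries-risk level, so the actual split is unknown.

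Nor is it right that ANOVA fails on binary data altogether. At 60/60 it holds its level; the fault is the pooled variance.

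Finally, the tested term is an inference. The SAP could mean a separate ANOVA within each risk group. Comparing the resulting p-values would not test whether the effect differs by risk, so that reading does not rescue the plan. No error rate was computed for it.

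**Conclusion.** The concern holds in a conditional form. On its natural reading, the SAP applies a pooled-variance method to a once-measured yes/no outcome. If treatment-by-risk is the tested term, the method misstates its error rate whenever filling rates and subgroup sizes both differ by caries risk. The direction depends on which group is larger: too many rejections if high-risk patients are the minority, too few and a loss of power if they are the majority. The second is the likelier case given section 4.2. The sizes in the working are illustrations under assumed rates and splits, not predictions. Because the SAP gives neither, the sponsor cannot tell in advance which way the test would err. This is a secondary analysis, so the point merits correction without calling the primary result into question.

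**What to change.** Replace the ANOVA phrase in the SAP with: *The treatment effect by baseline caries risk (preoperative assessment) is examined by comparing the within-patient risk difference between risk groups with an unequal-variance (Welch or robust-variance) test; paired risk differences with 95% CI are given per group; the analysis is exploratory.*

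The SAP should also state how the preoperative assessment is turned into risk groups, since no version of the test can be reproduced without that.

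If an odds-ratio scale is preferred (conditional logistic regression, or Fisher's exact test on the direction of discordant pairs by risk group), the SAP must say so, because it tests a different hypothesis. With the same 15-point risk difference in both groups (40% to 25% and 20% to 5%), Fisher's test rejects about 12% to 14% of the time at 60/60 and 30/90. It does so because the odds ratios differ although the risk differences do not. It also has less power with few discordant pairs: 21% against 56% for the unequal-variance test at 30/90 in the Step 5 scenario.

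The cost is one replaced sentence for the method and a short definition of the risk groups, with no new data or patients.
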